6.2 Dose escalation

- 6.2.1. The proposed study will follow a phase IA-B dose-escalation design wherein three SBRT dose levels targeting the primary tumor will be evaluated; level I: 6 Gy x 5 fractions (a common palliative dose), level II: 8 Gy x 5 fractions and level III: 10 Gy x 5 fractions (a common definitive dose).
- 6.2.2. Dose-limiting toxicity (DLT) will be defined as any grade 4 or higher toxicity that occurs within 30 days post MWA (approximately 90 days post SBRT) specifically: hemorrhage, hematoma, nephrotoxicity, gastric, duodenal or small bowel perforation or obstruction attributable to the radiation, the MWA or the combination of the treatment. Attributable DLT will be defined as that which is possibly, probably or definitely felt to be due to either radiation or ablation and occurring within the vicinity of the radiation treatment field (as reviewed by Drs. [name]/[name]) or in the vicinity of the microwave ablation (as reviewed by [name]). Grade 3 toxicity is not considered a DLT as it may be seen in routine, standard of care treatment. If progressive disease is found at the time of interval imaging and the patient is deemed ineligible for MWA, the patient will not be part of the cohort used for DLT analysis as his/her inclusion may falsely lower potential toxicity rates.
- 6.2.3. A standard, traditional 3+3 design will be utilized for dose escalation (Figure). For each three patient cohort, DLT will be assessed. In the case of 0/3 DLTs, the dose will be escalated to the next level. In the case of 2/3 DLTs, the dose escalation will be halted with the previous level being the MTD. In the case of 1/3 DLTs, an additional three patients will be enrolled at the current dose level. If no additional DLTs are seen, the dose will be escalated to the next level. In the event of a total of 2 or more DLTs in 6 patients, the dose escalation will be halted with the previous dose level being the MTD. Once the MTD has been established, the MTD will be used for the subsequent Phase IB expansion cohort.

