6.7 Duration of Therapy

Treatment with SBRT will be delivered over a period of two weeks, with radiation delivered two to three times per week. Four to six weeks after treatment, patients will be evaluated for microwave ablation by the treating radiologist with repeat CT or MRI imaging of the abdomen. Eight weeks after the conclusion of radiation treatment, patients will undergo microwave ablation, a single procedure. Adjuvant systemic treatment will be administered per institutional policies, physician recommendations, and patient preferences. Criteria for removal from study are described below.

6.8 Duration of Follow-Up: Refer to Table 2

After study enrollment, patients will undergo SBRT over a period of approximately 2 weeks. After 8 weeks, patients will undergo microwave ablation. Post treatment, patients will be followed as per standard of care. This will include a clinical visit four weeks after ablation, three months after ablation, six months after ablation, followed by visits every 6 months for a period of 3 years. Imaging will include either contrast-enhanced CT or MRI imaging at 3 and 6 months post therapy and every 6 months for 3 years. A BMP (including creatinine) will be obtained with imaging to evaluate renal function. Long term toxicity (specifically, nephrotoxicity, bowel obstruction, skin changes, and pain) will be assessed at these follow-up visits. Follow-up visits will be conducted by one of the treating physicians (radiation oncologist, interventional radiologist, or urologist) who will document physical exam, laboratory, and imaging findings as well as evaluate for toxicity. Any other evaluations prompted by symptoms, laboratory evaluation, or at the treating physicians' discretion may be performed as per standard of care. If a patient decides to withdraw from the study for non-treatment related reasons, no additional study-specific information will be obtained from the patient's future follow-up visit.

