Adverse event evaluation		X	X	X		X	X
B-hCG for WOCBP	X						
Research Biopsy ³	X				X		
Radiological evaluation/CT or MRI of Chest, Abdomen and Pelvis	X			X ⁵			X ⁵

¹: MWA will be approximately 8 weeks post XRT

²: Followup: 3 months and 6 months post MWA then every 6 month for 3 years, then annually

³: Research biopsy sampling will be done at the time of the diagnostic biopsy (if not yet performed at time of consent) and at during the microwave ablation procedure

⁴: Clinical diagnostic biopsy does not have a “window”. Patient must be treatment naïve for the renal cell carcinoma at time of study enrollment.

⁵: Imaging post ablation therapy will be at MD discretion, and in accordance with NCCN guidelines

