2. Is life threatening (places the subject at immediate risk of death)
3. Requires inpatient hospitalization or prolongation of existing hospitalization
4. Is a persistent or significant disability/incapacity
5. Is a congenital anomaly/birth defect
6. Any event that does not exactly meet this definition yet, in the investigator's opinion represents a significant hazard can be assigned the "other significant hazard" regulatory reporting serious criteria
7. Additionally, important medical events that may not be immediately life threatening or result in death or hospitalization but that may jeopardize the subject or require intervention to prevent one of the outcomes listed above, or result in urgent investigation, may be considered serious. Examples include allergic bronchospasm, convulsions, and blood dyscrasias.

Note: All deaths on treatment require both routine and expedited reporting regardless of causality. Attribution to treatment or other cause must be provided. "On treatment" is defined as during or within 30 days of completing protocol treatment (MWA).

All serious adverse events deemed to be related by the investigator to the SBRT or MWA (as listed in section 13.) will be collected and recorded throughout the study period beginning with the signing of the informed consent through the day patient is removed from the study or the date of death or three years after completion of the MWA (or the last SBRT treatment if surgery is not performed), whichever is earlier.

All serious adverse events that occur after the subject has signed the informed consent form must be reported to University of Wisconsin Carbone Cancer Center Data Safety and Monitoring Board and other regulatory agencies.

Serious adverse events occurring after conclusion of the study AND thought to be possibly related to the investigational study will be collected and reported within 10 working days of discovery or notification of the event via the same mechanism.

Table 3. Expedited reporting requirements for adverse events that occur within 30 days of the last protocol intervention.

FDA Reporting Requirements for Serious Adverse Events (21 CFR Part 312)
--

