Consult the UW-IRB website for reporting guidelines.

Other Reporting Requirements

Reporting to the FDA

Serious Adverse Events occurring on studies on which a UW PI is acting as sponsor-investigator must be reported to the FDA within the appropriate time frame. Mandatory and voluntary reporting guidelines and instructions are outlined on the FDA website:

<http://www.fda.gov/Safety/MedWatch/HowToReport/default.htm>

Expedited reporting requirements for adverse events that occur within 30 days of the last dose of radiation therapy¹

FDA Reporting Requirements for Serious Adverse Events (21 CFR Part 312)			

NOTE: Investigators MUST immediately report to the PI, UWCCC and UW IRB per policy ANY Serious Adverse Events, whether or not they are considered related to the investigational agent(s)/intervention (21 CFR 312.64). FDA Med Watch (3500A) will be submitted for grade 4 and 5 events at the discretion of the sponsor-investigator.
 
An adverse event is considered serious if it results in ANY of the following outcomes:
 
 7) Death. 8) A life-threatening adverse event. 9) An adverse event that results in inpatient hospitalization or prolongation of existing hospitalization for ≥ 24 hours. 10) A persistent or significant incapacity or substantial disruption of the ability to conduct normal life functions. 11) A congenital anomaly/birth defect. 12) Important Medical Events (IME) that may not result in death, be life threatening, or require hospitalization may be considered serious when, based upon medical judgment, they may jeopardize the patient or subject and may require medical or surgical intervention to prevent one of the outcomes listed in this definition (FDA, 21 CFR 312.32; ICH E2A and ICH E6). 			

ALL SERIOUS adverse events that meet the above criteria* MUST be immediately reported to the UWCCC within the timeframes detailed in the table below: With the exception of a 24 hr hospitalization for MWA procedure
			
Hospitalization	Grade 1 and Grade 2 Timeframes	Grade 3 Time Frames	Grade 4 & 5 Timeframes
Resulting in hospitalization ≥ 24 hrs	Not required	10 Calendar Days	24 Hour; 5 Calendar Days
Not resulting in Hospitalization ≥ 24 hrs	Not required	10 Calendar Days	

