
 • See section 13.0 for listing of toxicities • Grade 3 toxicities during the 24hr hospitalization for MWA are exemption from SAE reporting 
Expedited AE reporting timelines are defined as:
 
 • 24-Hour; 5 Calendar Days – The AE must initially be reported within 24 hours of learning of the AE, followed by a complete expedited report within 3 calendar days of the initial 24-hour report. • 10 Calendar Days – A complete expedited report on the AE must be submitted within 5 calendar days of learning of the AE 			

¹ Serious adverse events that occur more than 30 days after the last administration of investigational intervention and have an attribution of possible, probable, or definite require reporting as follows:
 
Expedited 24-hour notification followed by complete report within 10 working days for:
 
 • All Grade 4, and 5 AEs

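### Appendix 2 closes its expedited-reporting window 30 days after the last radiation dose, about 26 days before ablation, and so conflicts with Table 3

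*Combined protocol and SAP*

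**What the plan says.** The plan contains two nearly identical expedited-reporting tables.

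- **Section 13.4, Table 3** is headed "Expedited reporting requirements for adverse events that occur within 30 days of the last protocol intervention". The same section treats MWA as the completion of protocol treatment.
- **Appendix 2** (the cancer center's data safety monitoring plan) heads its table "Expedited reporting requirements for adverse events that occur within 30 days of the last dose of radiation therapy". Earlier in the appendix, staff are told to find the reporting timeline for an SAE from a table given there.
- **Body of the Appendix 2 table.** Like Table 3, it exempts a 24-hour hospital stay for MWA, and grade 3 toxicities during that stay.
- **Footnote 1 of the Appendix 2 table** covers later events: "Serious adverse events that occur more than 30 days after the last administration of investigational intervention and have an attribution of possible, probable, or definite". For these it asks for 24-hour notice and a complete report within 10 working days, for grades 4 and 5 only.
- **Timing of MWA.** Section 6.7 states: "Eight weeks after the conclusion of radiation treatment, patients will undergo microwave ablation, a single procedure". A note to the study calendar (Table 2) gives the same interval as approximate, and Section 6.1 says two months.
- **DLT period.** Section 6.2.2 ends it "within 30 days post MWA (approximately 90 days post SBRT". Sections 7.1.1 and 9.3.1 also run it to 30 days after ablation.

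**The concern.** Treatment has two stages, and the two headings start the 30-day clock at different stages. For a patient who has no MWA, radiation is the last intervention and the headings agree. For every patient who reaches MWA they disagree, and the disagreement falls on the ablation and the month after it.

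That month matters because Section 6.2.4 holds the next dose level until DLTs have been evaluated 30 days after ablation. What is at stake is how quickly SAEs in this period reach the center and its safety committee. A coordinator working from Appendix 2 alone could conclude that an SAE shortly after MWA lies outside the expedited table, while one working from Table 3 would apply a fixed deadline to the same event.

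**Working it through.** **Inputs**

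- Interval from last radiation fraction to MWA: 8 weeks (Section 6.7, Table 2); two months in Section 6.1, taken as 60 to 61 days.
- Appendix 2 window: 30 days from last radiation dose.
- Table 3 window: 30 days from last protocol intervention (MWA).

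Day 0 is the last radiation fraction.

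**Step 1. Reproduce the plan's own figure.** MWA falls on day 8 × 7 = 56, and 56 + 30 = 86. With the two-month reading, 60 + 30 = 90 and 61 + 30 = 91. Both agree with the approximate 90 days in Section 6.2.2.

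**Step 2. Compare the windows.**

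| | MWA at 8 weeks | MWA at two months |
|---|---|---|
| MWA | day 56 | day 60-61 |
| Appendix 2 window closes | day 30 | day 30 |
| Gap from closure to MWA | 56 − 30 = 26 days (3.7 weeks) | 30-31 days (4.3-4.4 weeks) |
| Table 3 window closes | day 86 | day 90-91 |
| Difference in closing day | 86 − 30 = 56 days | 60-61 days |

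The post-MWA part of the DLT period (days 56 to 86) does not overlap the Appendix 2 window at all.

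**Step 3. Test the Appendix 2 heading against its own table.** The exemptions for the MWA stay apply on about day 56. A window that closes on day 30 would leave them nothing to exempt, so the heading and the body cannot both be right.

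**Step 4. See whether footnote 1 closes the gap.** It does not name the intervention from which it counts.

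| Event after day 30, up to about day 86 | Footnote counted from radiation | Footnote counted from MWA | Table 3 |
|---|---|---|---|
| Grade 4-5 SAE, at least possibly related | 24-hour notice; complete report in 10 working days | Under neither heading nor footnote | 24-hour notice; complete report in 5 calendar days |
| Grade 4-5 SAE, not judged related | Not covered | Under neither | 24-hour notice; complete report in 5 calendar days |
| Grade 3 SAE (outside the exempt MWA stay) | Not covered | Under neither | 10 calendar days |

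On the first reading Appendix 2 keeps one of the three rows; on the second it keeps none.

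**Step 5. Compare the deadline definitions.** Both tables use the same two labels, one for 24 hours plus 5 calendar days and one for 10 calendar days. Table 3 defines them as 5 and 10 days. Appendix 2 defines them as 3 and 5 days, which contradicts its own labels. Changing the heading would leave this second conflict in place.

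**The case against.** The strongest reply is that little would be missed in practice. Table 3 stays in force. The oversight text in Appendix 2 takes its 24-hour and 10-day categories from the protocol. All SAEs go to the safety committee chair, and any SAE goes immediately to the principal investigator, the cancer center and the ethics board, related or not. Section 13.4 requires expedited reporting of every death within 30 days of MWA.

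This stands, and it rules out several stronger readings that a reader might infer:

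- **That DLTs escape expedited reporting.** A DLT is grade 4 or higher and at least possibly related. If footnote 1 is counted from radiation, a DLT that is an SAE keeps its 24-hour notice. It drops out of Appendix 2 only if the footnote is counted from MWA, and Table 3 covers it even then.
- **That grade 3 SAEs after the MWA stay have no deadline.** They have none in Appendix 2, but Table 3 gives them 10 calendar days.
- **That the whole DLT period is excluded.** DLTs may be attributed to radiation, and the period includes time before MWA, so the first 30 days after radiation lie in both windows. Only the post-MWA part is wholly outside.
- **That the named DLTs are likely around ablation.** Section 13.2 lists hemorrhage and hematoma as less likely, and bowel perforation and nephrotoxicity as rare.
- **That escalation decisions would miss DLTs.** Section 13.4 collects adverse events through the 30-day post-MWA visit, and Section 6.2.4 requires DLT evaluation before the next level opens. The issue is speed of notice, not the DLT count.

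The reply does not make the two headings agree. The general duties in Section 13.4 and Appendix 2 mostly lack a calendar deadline, and the instruction to report immediately in Appendix 2 sits inside the table with the faulty heading.

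**Conclusion.** The Appendix 2 heading is wrong as written. Its window closes 26 days before MWA (30 to 31 on the two-month reading) and 56 days before Table 3's. It contradicts both Table 3 and the MWA exemptions in its own table.

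The exposure is conditional on staff following Appendix 2 alone. They would then lose Table 3's calendar deadlines for grade 3 SAEs and unrelated grade 4-5 SAEs around MWA. If footnote 1 is counted from MWA, related grade 4-5 SAEs from day 31 to about day 86 are lost as well.

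This is a drafting inconsistency in an operational safety rule. It does not alter the design, the DLT definition or the sample size, but it should be corrected. The day counts assume that MWA takes place at about the planned interval; the conflict itself does not depend on the exact day, provided MWA falls more than 30 days after radiation.

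**What to change.** Preferably, delete the expedited-reporting table from Appendix 2 and refer to Table 3 in Section 13.4. That removes both the conflicting window and the conflicting deadline definitions.

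If the table is kept:

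1. Head it as Table 3 is headed, 30 days after the last protocol intervention, and state that this means MWA, or the last radiation treatment if MWA is not done. Section 13.4 already makes a similar provision for its three-year SAE collection.
2. Say in footnote 1 which intervention starts the clock, so that no event falls between heading and footnote.
3. Reconcile the deadline definitions: 3 and 5 calendar days in Appendix 2 against 5 and 10 in Table 3.

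The cost is a wording change to one appendix table, with no effect on treatment, visits, sample size or analysis.
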